8.4.2 UNANTICIPATED PROBLEM REPORTING

The investigator will report unanticipated problems (UPs) to the reviewing sIRB and to the DCC/lead principal investigator (PI). The UP report will include the following information:

- Protocol identifying information: protocol title and number, PI's name, and the IRB project number;
- A detailed description of the event, incident, experience, or outcome;
- An explanation of the basis for determining that the event, incident, experience, or outcome represents a UP;
- A description of any changes to the protocol or other corrective actions that have been taken or are proposed in response to the UP.

To satisfy the requirement for prompt reporting, UPs will be reported using the following timeline:

- Unanticipated problems that are SAEs will be reported to the DCC/study sponsor within 24 hours of the investigator becoming aware of the event, and a determination will be made in regard to their relation to the study drug. Those SAEs considered to be related to the study drug will be reported to the sIRB within 7 days of occurrence. Those SAEs not related to the study drug will be reported to the sIRB in annual reports. SAEs considered related to the study drug will be reported to the IRB and to the sIRB within 7 days.
- Any other UP will be reported to the DCC/study sponsor within 48 hours of the investigator becoming aware of the problem and will be reported to the sIRB annually.
- All UPs should be reported to appropriate institutional officials (as required by an institution's written reporting procedures), the supporting agency head (or designee), and the Office for Human Research

Protections (OHRP) within 7 days of the sIRB's receipt of the report of the problem from the investigator.

- For more information on sIRB reporting requirements, The JHM IRB Organizational Policy on Prompt Reporting of Reportable Events can be referenced here:

https://www.hopkinsmedicine.org/institutional_review_board/guidelines_policies/organization_policies/prompt_reporting_policy.html

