8.4 UNANTICIPATED PROBLEMS

8.4.1 DEFINITION OF UNANTICIPATED PROBLEMS (UP)

The Office for Human Research Protections (OHRP) considers unanticipated problems involving risks to participants or others to include, in general, any incident, experience, or outcome that meets all of the following criteria:

- Unexpected in terms of nature, severity, or frequency given (a) the research procedures that are described in the protocol-related documents, such as the single IRB (sIRB)-approved research protocol and informed consent document; and (b) the characteristics of the participant population being studied;
- Related or possibly related to participation in the research (“possibly related” means there is a reasonable possibility that the incident, experience, or outcome may have been caused by the procedures involved in the research); and
- Suggests that the research places participants or others at a greater risk of harm (including physical, psychological, economic, or social harm) than was previously known or recognized.

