10.1.10 PROTOCOL DEVIATIONS

A protocol deviation is any noncompliance with the clinical trial protocol, or Manual of Procedures (MOP) requirements. The noncompliance may be either on the part of the participant, the investigator, or the study site staff. As a result of deviations, corrective actions are to be developed by the site and implemented promptly.

It is the responsibility of the site investigator to use continuous vigilance to identify and report deviations within the required number of working days of identification of the protocol deviation. All deviations must be addressed in study source documents, reported to the NIA Program Official and Johns Hopkins TIC Data Coordinating Center. Protocol deviations must be sent to the reviewing sIRB per their policies. The site investigator is responsible for knowing and adhering to the reviewing sIRB requirements. Further details about the handling of protocol deviations will be included in the MOP.

Emergency deviations require reporting to the sIRB promptly after they occur

Emergency deviations are those occurring in an emergency situation, such as when a departure from the protocol is required immediately to protect the life or physical well-being of a participant. In such cases there is no time to prospectively seek the approval of the IRB. The sponsor and the sIRB must be notified as soon as possible, but not later than 5 days after the emergency situation occurred (21 CFR 812.150(a)(4)). Deviations of this nature are always considered to be unanticipated problems involving risks to participants or others (see JHM IRB Policy No. 103.6(b)).

Major, non-emergent deviations require approval by the sIRB before they occur

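### Section 8.4.2 sends unanticipated problems that are not SAEs, or are SAEs judged unrelated to the study drug, to the single IRB only once a year, and does not acknowledge the 5-day limit for emergency deviations in 10.1.10

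*Protocol*

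**What the plan says.** Section 8.4.1 sets three criteria for an unanticipated problem, all of which must be met: the event is unexpected, it is related or possibly related to taking part in the research, and it "Suggests that the research places participants or others at a greater risk of harm" than was known before.

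Section 8.4.2 opens its schedule with "To satisfy the requirement for prompt reporting, UPs will be reported using the following timeline". It then gives these routes to the sIRB:

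- UPs that are SAEs go to the coordinating center and sponsor within 24 hours. After that, "Those SAEs considered to be related to the study drug will be reported to the sIRB within 7 days of occurrence". Those judged not related to the drug go to the sIRB in annual reports.
- Every remaining UP goes to the coordinating center and sponsor inside 48 hours. For the sIRB, the same sentence sets only a yearly report: "becoming aware of the problem and will be reported to the sIRB annually".
- Institutional officials, the supporting agency and OHRP are told "within 7 days of the sIRB's receipt of the report of the problem from the investigator".

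Section 10.1.10 covers emergency deviations. It states: "The sponsor and the sIRB must be notified as soon as possible, but not later than 5 days after the emergency situation occurred". It adds: "Deviations of this nature are always considered to be unanticipated problems involving risks to participants or others".

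Section 8.4.3 requires sIRB and DSMB approval of a letter to participants when a drug-related UP could change the risk of participation. It gives no deadline.

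**The concern.** An annual report does not fit a schedule whose stated purpose is prompt reporting. The events on the annual route are also not trivial, because 8.4.1 makes increased risk a condition of being a UP at all. For comparison, 10.1.10 reserves reporting at continuing review for minor or administrative deviations, which by its own definition do not touch participants' safety, rights or welfare. Section 8.4.2 thus gives events that signal new risk a similarly slow, periodic route.

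At stake is how soon the body that approves the consent form and the continuation of the study sees such an event. A second issue is that two sections of the same protocol give a site different sIRB instructions for an emergency deviation.

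**Working it through.** No sample-size, power or alpha figure is involved. The check sets the reporting limits side by side. The one assumption is that annual means up to about 365 days.

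| Event | To coordinating center/sponsor | To sIRB | Source |
|---|---|---|---|
| UP, SAE, drug-related | 24 hours | 7 days | 8.4.2 |
| UP, SAE, not drug-related | 24 hours | up to about 365 days | 8.4.2 |
| UP, not an SAE | 48 hours | up to about 365 days | 8.4.2 |
| Emergency deviation (always a UP) | sponsor: 5 days | 5 days | 10.1.10 |

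**Step 1: what the annual route carries.** Section 8.4.1 turns on relation to the research, while the split of SAEs in 8.4.2 turns on relation to the drug. An unexpected serious event caused by a study procedure such as imaging or phlebotomy can therefore satisfy 8.4.1, be judged unrelated to the drug, and reach the sIRB only in the annual report. Non-SAE events can qualify as well, because 8.4.1 counts psychological, economic and social harm alongside physical harm.

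**Step 2: the downstream clock.** OHRP and institutional officials have 7 days counted from sIRB receipt. On the annual route the latest date is about 365 + 7 = 372 days.

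**Step 3: the overlap with 10.1.10.** An emergency deviation is by rule a UP.

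- If it is not an SAE, or is an SAE unrelated to the drug, 8.4.2 gives the annual route and 10.1.10 gives at most 5 days.
- If it is a drug-related SAE, 8.4.2 gives 7 days against 5 in 10.1.10.

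Section 8.4.2 contains no exception for emergency deviations and no pointer to 10.1.10.

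**Step 4: other ways the sIRB might hear sooner.**

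- Section 8.4.3 covers only UPs related to the study drug and states no deadline.
- Section 8.3.7 provides for a letter, in consultation with the DSMB and sIRB, on new information about the study drug. It also states no deadline.
- Section 8.3.6 has the sponsor notify the IRB within 7 calendar days of suspected unexpected serious reactions. These are drug-related by definition, so they are not on the annual route.

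None of these sets an sIRB deadline for a UP that arises from another study procedure.

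**The case against.** The strongest reply is that the two sections can both be obeyed. Section 10.1.10 is the specific rule for emergency deviations and 8.4.2 is the residual rule. Nothing in 8.4.2 suspends the 5-day limit, so a site that waited a year would breach 10.1.10. This stands. A reader might infer that any UP faces a choice between 5 days and 12 months, but the documents do not support that. The 5-day limit applies only to emergency deviations, where the stricter rule still binds. For other UPs on the annual route, 8.4.2 is the only sIRB deadline stated, and the problem is the interval itself.

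A reader might also infer that participants could stay uninformed for most of their 18 months of follow-up. That is not shown. The letters in 8.4.3 and 8.3.7 are triggered by the emergence of the information and do not wait for the annual report. Section 8.3.6 requires the sponsor to notify FDA and participating investigators of potential serious risks within 15 calendar days. Under 10.1.6 the DSMB meets at least semiannually and has access to all study data. The coordinating center and sponsor hear within 24 to 48 hours.

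Finally, it cannot be said that a site reporting only annually would be compliant. Section 8.4.2 links to the sIRB's own prompt-reporting policy, whose content is not in the protocol. The policy may be stricter, but 8.4.2 offers it for further information and does not say that it overrides the written interval.

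These points narrow the finding. They do not explain an annual sIRB route inside a prompt-reporting schedule, or the missing link to 10.1.10.

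**Conclusion.** The point holds as a defect in safety-reporting text. Two classes of UP go to the sIRB only annually under 8.4.2: those that are not SAEs, and those that are SAEs judged unrelated to the study drug. On the stated reading of annual, the outer limits are about 365 days for the sIRB and about 372 days for OHRP and institutional officials. These are worst cases under the wording, not expected delays. The emergency-deviation subset has a separate 5-day limit that 8.4.2 does not mention.

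The delay concerns the sIRB and the bodies whose clock it starts. It does not mean that all oversight is uninformed. The point has no bearing on the estimand, the analysis or data integrity. It is minor in rank, but it is relevant to safety and easy to settle.

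**What to change.** In 8.4.2, replace the annual sIRB route with an expedited one for every event that meets the 8.4.1 definition, including UPs that are SAEs not related to the study drug. The sponsor should set the limit with the sIRB, consistent with the sIRB policy already linked there. Add a cross-reference to 10.1.10 and reconcile the limits so that an emergency deviation has one sIRB deadline wherever a site looks. Align 8.4.3 with the same timeline, so that the participant-letter process starts from the expedited report.

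The cost is a wording amendment and a few more expedited reports. Design, sample size and analysis are unaffected.

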8.4.3 REPORTING UNANTICIPATED PROBLEMS TO PARTICIPANTS

If UPs possibly, probably, or definitely related to the study drug appear in the literature, other studies, or this study, which could change the risk of the study participation, the investigators will draft a letter to all participants describing this new information, the likelihood that it is related to the study drug, how this information alters the risk to participate in the study, and new measures taken to ensure the safety of participants. This process will be done with review and approval of the sIRB and DSMB. In addition, this new information will be added to the consent form and study participants already enrolled will be re-consented.

9 STATISTICAL CONSIDERATIONS

9.1 STATISTICAL HYPOTHESES

Primary efficacy endpoint(s)

The primary aim is to compare changes from baseline to 18 months in verbal memory performance, measured with the Total Recall Score of the Free and Cued Selective Reminding Test (FC-SRT), between the metformin and placebo arms, following an ITT approach. We hypothesize that the metformin arm will demonstrate less decline in the FC-SRT as compared with placebo.

Secondary efficacy endpoint(s):

- Examine global cognitive performance, measured with the Alzheimer's Disease Cooperative Study, Preclinical Alzheimer Cognitive Composite (ADCS-PACC). We hypothesize that the metformin arm will demonstrate less decline or improvement in the ADCS PACC as compared with placebo.
- Examine APOE-ε4 genotype as a modifier of the efficacy of metformin. We hypothesize that the benefit of metformin will be highest among APOE-ε4 carriers.
- Compare changes in neurodegeneration, ascertained as cortical thickness in areas affected by Alzheimer's disease acquired on brain MRI from baseline to 18 months between metformin and placebo. We hypothesize that the metformin arm will show less decrease in cortical thickness at 18 months compared with placebo.
- Compare changes in cerebrovascular disease, ascertained as white matter hyperintensities (WMH) volume on brain MRI, from baseline to 18 months between metformin and placebo. We hypothesize that the metformin arm will show less increase in WMH as compared with the placebo arm.
- Compare changes in whole brain Aβ standardized uptake value ratio (SUVR) and in incident amyloid positivity from baseline to 18 months between the metformin and placebo arms.
- Compare changes in tau SUVR in a composite brain region comprising medial and inferolateral temporal cortex from baseline to 18 months between the metformin and placebo arms.
- Compare changes in plasma AD biomarkers between metformin and placebo.

9.2 SAMPLE SIZE DETERMINATION

9.2.1. Original Sample size calculation. Sample size has been calculated for the difference in average change in SRT scores at 24 months from baseline between metformin and placebo arms. In the previous study, MetMCI, average change in SRT score at 12 months among metformin subjects was 9.8 (SD = 8.6) versus 5.9 (SD = 8.5) in the placebo arm, which corresponds to a standardized difference in means measured as Cohen's D of 0.46 (90%CI: 0.06 to 0.86). In the placebo arm, average change in SRT was similar at 12 months and 9 months. However, in the metformin arm, average SRT continued to improve from 9 to 12 months. These data are based on 33 (82.5%) vs. 37 (92.5%) subjects with non-missing outcome data at 12 months in metformin and placebo arms, respectively. Assuming that a similar standardized difference in means will be observed at 24 months, our calculation indicates that we will need 87 participants per arm to detect this effect size with 90% power, rejecting the null hypothesis at 0.08 level of statistical significance. This observed standardized difference corresponds to a "medium" effect size (Cohen, 1988). If, however, the observed difference at 24 months corresponds to low-to-medium effect sizes (i.e., Cohen's D between 0.35 and 0.4), the required maximum sample size is 302. The selected total sample size of 370 participants will be adequate to detect effect sizes 0.35 and larger, assuming overall drop-out/missingness of about 20%. Since the only difference between treatment arms was observed in APOEe4 negative participants, we performed sample size calculations for this subgroup. The observed standardized difference in average change in SRT score between metformin and placebo at 12 months was 0.6, (90%CI: 0.13 to 1.07). With a sample size of 302 (or adjusted for missing at 370) and assuming 60% participants will be APOEe4 negative, we will have 90% statistical power to detect this effect size or larger by rejecting the null hypothesis at 0.01 level of statistical significance.


only ApoE- ϵ 4 negative patients. The power for the overall sample was based on a type I error of 0.08, while a type I error rate of 0.01 was used for the ApoE- ϵ 4 negative participants. An additional alpha of 0.01 was allocated for the ApoE- ϵ 4 positive patients; however, simulations were not undertaken for this patient population, since there was no preliminary evidence of a treatment effect among the ApoE- ϵ 4 positive patients. Based on these data simulations, we estimate a power of 92.4% to statistically detect a larger FC-SRT slope in the metformin group as compared to the FC-SRT slope among the placebo arm (e.g. 9240 out of 10,000 samples produced a significant interaction model term at the alpha = 0.08 level in the regression analysis). Similarly, we found an estimated power of 97.8% to detect a statistically larger FC-SRT slope in the metformin versus placebo groups among the ApoE- ϵ 4 negative patients at alpha = 0.01 level. The proportion of ApoE- ϵ 4 negative patients ranged from 67% to 79% among the 10,000 simulated samples, as compared to a proportion of 73.8% for the ApoE- ϵ 4 negative patients (59 of 80) in the preliminary study.

Given these power analyses, the study team is confident that the reduction in sample size from 370 to 326 will not compromise the goals of the study.

9.3 POPULATIONS FOR ANALYSES

The population for analyses will be all 326 randomized participants based on an intent to treat approach.

9.4 STATISTICAL ANALYSES

9.4.1 GENERAL APPROACH

Exploratory data analysis will be performed on the entire study sample. All variables will be checked for outlying and unusual observations to detect general patterns, identify gaps and inconsistencies in the data. Visual inspection will be performed by means of box plots, scatterplots, quantile plots and others. Outliers will be checked for possible data entry errors. Reported descriptive statistics for continuous variables will include the number of participants with non-missing observations, median, mean, SD, interquartile range and range, while statistics for categorical variables will include the frequency and percentage of participants in each category.

Adjustment for covariates. In the primary analysis, all models described below will be adjusted for, ApoE- ϵ 4 (as a binary indicator), age (continuous), self-reported sex (male or female) (categorical), baseline total recall FC-SRT score (continuous), MMSE score (continuous), BMI (continuous) and HbA1c level. Additional adjustment for site, BMI, gender, race, educational attainment, COVID-19 history, and white matter hyperintensity will be done as sensitivity analyses. Statistical tests will be two-sided.

